8.4.9. Treatment of adverse events

Treatment of any AE is at the sole discretion of the investigator and according to current good medical practice. Any medication administered for the treatment of a SAE/AESIs should be recorded in Expedited Adverse Event Report of the subject's eCRF (refer to Section 7.5).

8.4.10. Subject card

Study subjects/subjects' parent(s)/LAR(s) must be provided with the address and telephone number of the main contact for information about the clinical study.

The investigator (or designate) must therefore provide a "subject card" to each subject/subject's parent(s)/LAR(s). In an emergency situation, this card serves to inform the responsible attending physician that the subject is in a clinical study and that relevant information may be obtained by contacting the investigator.

Subjects/subjects' parent(s)/LAR(s) must be instructed to keep subject cards in their possession at all times during the study duration.

8.5. Genetic Research (Pharmacogenetics)

Genetics are not evaluated in this study.

8.6. Study conclusion

- The study termination call will occur on study Day 451 (after safety follow up call 7) *or (Day 271 [Month 9]) for subjects who have not reached Day 271 [Month 9] at the time this amendment takes effect.* The termination visit will be a phone call *(Amended 11 October 2022)*.
- The date of termination is the date of the last contact (clinic visit or telephone call) in which the subject's health status was assessed or, in cases where the subject does not agree to any further safety follow-up, it is the date consent is withdrawn. This date should be recorded on the termination eCRF page. For visit procedures to be performed for a subject whose planned study participation ends prematurely, please see below.

- At the Termination visit, the following procedures will be performed: interview of subject and/or parent(s)/LAR(s) to collect any medically attended AEs, AEs leading to withdrawal, AESI, SAEs, and/or concomitant medications/vaccinations. Any concomitant medications associated with those events will also be collected and recorded in the subject's records and on the eCRF.
- The site will review with the subject and/or parent(s)/LAR(s) the plan of when information relating to the subject's participation in the study may be available (e.g., study results, treatment assignments). It will also be discussed how information relating to the subject's participation in the study will be shared with the subject's healthcare provider if the subject and/or parent(s)/LAR(s) chooses to share this information or if it is required by local regulations.
- The site will complete the termination eCRF page and this will mark the completion of the subject's participation in the study.

8.6.1. Early Termination

When a subject is withdrawn from treatment or withdraws from the study, the investigator will notify the Sponsor and, when possible, will perform the procedures listed below. The reason(s) for the early termination will be included in the subject's source documentation.

During the telephone call, the following procedures will be performed:

- review of Subject eDiary (if applicable).
- interview of subject and/or parent(s)/LAR(s) to collect unsolicited AEs, medically attended AEs, AEs leading to withdrawal, SAEs, AESI.
- interview of subject and/or parent(s)/LAR(s) to collect concomitant medications/vaccinations administered to treat AEs collected in the study.

Additionally, the following 2 procedures will be performed at the clinic visit:

- perform a symptom-directed physical assessment (including e.g., measurement of vital signs, body temperature [preferably oral] and a check of general appearance).
- blood sampling to test immunogenicity (if withdrawal occur at or prior to Visit 4 [study Day 91]).

If the Early Termination Visit is a telephone call, collect as much information as possible. Early Termination Visits include subjects who were randomized but not treated.

The site will review with the subject and/or parent(s)/LAR(s) the plan of when information relating to the subject's participation in the study may be available (e.g., study results, treatment assignments). It will also be discussed how information relating to the subject's participation in the study will be shared with the subject's healthcare provider, if the subject and/or parent(s)/LAR(s) chooses to share this information.

The site will complete the termination eCRF page and this will mark the completion of the subject's participation in the study.

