7.7. Contraindications to subsequent vaccine(s) administration

Prior to receipt of additional study vaccination, subjects must be evaluated to confirm that they are eligible for subsequent vaccination. If subjects meet any of the original exclusion criteria or the criteria listed below, they should not receive additional vaccinations. However, these subjects should be encouraged to continue study participation.

- Anaphylaxis following the administration of vaccines
- Pregnancy (see Section 12.5.7.1)
- Any condition that in the judgment of the investigator would make IM injection unsafe.

- Any occurrence of an event listed in the exclusion criteria which must be always re-assessed by the investigator before administration of the second dose of study vaccine.
- Subjects who experience any serious adverse event (SAE) judged to be possibly or probably related to study vaccine or non-study vaccines, including hypersensitivity reactions.
- Subjects who develop any new condition which, in the opinion of the investigator, may pose additional risk to the subject if he/she continues to participate in the study.
- Occurrence of a new AESI or the exacerbation of an existing AESI. Refer to Section [12.5.5](#) for the definition of AESIs.

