Investigators will apply due diligence to avoid protocol deviations. Under no circumstances should the investigator contact GSK or its agents, if any, monitoring the study to request approval of a protocol deviation, as no authorized deviations are permitted. If the investigator feels a change to the protocol would improve the conduct of the study this must be considered a protocol amendment, and unless such an amendment is agreed upon by GSK and approved by the IRB/EC and health authorities it cannot be implemented.

Any subject who becomes pregnant during the study, despite the protocol requirement for highly effective method of contraception, will not receive further vaccinations but should be encouraged to continue participating in the study for safety follow-up. The site must complete a Pregnancy Report eCRF (initial report) as soon as possible after learning of pregnancy occurrence (see Section 12.5.8 for further details). If the subject withdraws from the study for any of the above categories except death, the site will obtain permission from the subject to continue to remain in contact with her until the outcome of the pregnancy is known, even if the outcome is not known until after the subject reaches the end of follow-up period.

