9.2. Discontinuation of study vaccine(s)

A 'withdrawal' from the study vaccine(s) refers to any subject who does not receive the complete treatment, i.e. when no further planned dose is administered from the date of withdrawal. A subject withdrawn from the study vaccine(s) may continue further study procedures (safety or immunogenicity) if planned in the study protocol, as deemed appropriate by the investigator.

Primary reason relative to premature discontinuation of the study vaccine(s) will be documented on the Vaccine Administration page/screen of the eCRF. The investigator will document whether the decision to discontinue further vaccination/treatment was made by the subject himself/herself, by the subject's parent(s)/LAR(s), or by the investigator, as well as which of the following possible reasons was responsible for withdrawal:

- Adverse event requiring expedited reporting
- Non-serious AE (specify)
- Unsolicited non-serious AE
- Solicited adverse event
- Not willing to be vaccinated
- Other (specify).

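### Protocol Section 8.6.1 closes out subjects who only stop vaccination, contradicting Sections 7.7, 9.1, 9.2 and 12.5.7.1, and can cut off active safety follow-up before Month 9

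*Protocol*

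**What the plan says.** Section 8.6.1 of the protocol (Early Termination) has two triggers joined by one conjunction: "When a subject is withdrawn from treatment or withdraws from the study, the investigator will notify the Sponsor". The procedures that follow make no distinction between them: interview, diary review, symptom-directed examination, and a blood draw if the withdrawal is no later than Visit 4. The section closes with "The site will complete the termination eCRF page and this will mark the completion of the" subject's participation.

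Four other places treat stopping vaccine as something a subject can do while remaining in the study:

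- Section 7.7, on subjects barred from further doses: "However, these subjects should be encouraged to continue study participation".
- Section 9.1, on a subject who becomes pregnant: she "will not receive further vaccinations but should be encouraged to continue participating in the study for safety follow-up".
- Section 9.2: "A subject withdrawn from the study vaccine(s) may continue further study procedures (safety or immunogenicity) if planned in the study protocol", subject to the investigator's judgement.
- Section 12.5.7.1 lets pregnant or lactating subjects go on with other procedures at the investigator's discretion.

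Sections 9.1 and 9.2 also define withdrawal from the study and withdrawal from vaccine as two separate states. Section 8.6 introduces 8.6.1 with a narrower scope: "For visit procedures to be performed for a subject whose planned study participation ends prematurely, please see below".

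**The concern.** A site cannot both close a subject and keep that subject. The reasons for barring further doses in Section 7.7 include a related SAE, a new or worsening AESI, pregnancy, and a new condition that adds risk. If 8.6.1 is applied to these subjects, the loss of follow-up is linked to safety outcome, and handling may differ between sites according to which section is read first.

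The primary safety endpoints cover SAEs, AEs leading to withdrawal, medically attended AEs and AESIs from Day 1 to Month 9. They are reported as percentages of subjects on the Exposed Set (Protocol Section 10.3.4; SAP Section 5.5.1.3), with no stated adjustment for time under observation. A subject closed early stays in the denominator, while later events are no longer actively sought. The bias is towards too few events, in the subjects about whom further safety information is most wanted.

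**Working it through.** **1. The passages side by side**

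| Protocol section | Subject who stops vaccine only |
|---|---|
| 8.6.1 | Early Termination; termination page; participation over |
| 8.6 (lead-in) | Points to 8.6.1 only where participation ends early |
| 7.7 | Encouraged to continue |
| 9.1 (pregnancy) | Encouraged to continue for safety follow-up |
| 9.2 | May continue, investigator's judgement |
| 12.5.7.1 (pregnancy, lactation) | May continue, investigator's discretion |

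Only the operative sentence of 8.6.1 treats stopping vaccine as a reason to close the subject. The wording of 7.7, 9.1 and 9.2 encourages or permits; it does not expressly override 8.6.1.

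**2. Safety follow-up lost if 8.6.1 is applied**

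Inputs: Month 9 is SFU 5 at Day 271 (Table 3), so the period from Day 1 is 271 − 1 = 270 days. For closure on Day d, days lost = 271 − d, and the share lost = (271 − d)/270.

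- Day 10 (example of a stop soon after dose 1): 271 − 10 = 261; 261/270 = 97%
- Day 61 (Visit 3): 271 − 61 = 210; 210/270 = 78%
- Day 91 (Visit 4): 271 − 91 = 180; 180/270 = 67%

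These are losses per affected subject. The documents give no rate of stopping vaccination.

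**3. Which immunogenicity samples are at risk**

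Inputs: Visit 2 is allowed 23–58 days after Visit 1, and Visit 4 is allowed 23–58 days after Visit 3 (Table 4). SAP Table 4, code 2090, removes off-schedule samples from the per-protocol set at Month 1 or Month 3. Assume the termination draw is taken.

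- Stop and draw less than 23 days after dose 1: the draw precedes the Visit 2 window, and a valid Month 1 sample is lost.
- Stop at Visit 3: the Month 1 sample has already been taken. In the two arms of the MenB comparison the second rMenB+OMV NZ dose has not been given, so there is no valid Month 3 titre to lose.
- Stop and draw less than 23 days after the Visit 3 dose: the draw precedes the Visit 4 window, and a valid Month 3 sample is lost.
- Stop at Visit 4: the sample is drawn before vaccination, so nothing is lost.

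The SAP gives no rule for assigning an early-termination sample to a visit.

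**4. Effect on power**

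The plan's own figure first. Each test is a two-sample non-inferiority test on the log10 scale, one-sided 0.025, with n per group, noncentral t on 2n − 2 degrees of freedom and noncentrality [log10(0.9) − log10(0.5)] / [SD × √(2/n)]. SDs are the Est_sd column of Protocol Table 19. At n = 250 the products over four tests are 96.81%, 98.47% and 94.65%. Overall: 0.9681 × 0.9847 × 0.9465 = 90.23%, which equals Table 23.

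Then suppose, as an assumption, that evaluable subjects are lost from every group below 250:

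- 1 lost (n = 249): 90.04%
- 3 lost (n = 247): 89.65%
- 5 lost (n = 245): 89.25%

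Even five per group costs about one percentage point (90.23 − 89.25 = 0.98). Enrolment of 315 per group already allows for about 20% not evaluable (315 × 0.8 = 252).

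**The case against.** The best defence is that the intent is clear. The lead-in in 8.6 confines 8.6.1 to participation that ends early. Section 9.1 counts a subject as a study withdrawal only when nothing further is done or collected. Section 9.2 records stopping vaccine on a different eCRF page. On this view there is one loose phrase against several consistent passages, and sites will read it correctly. That is probably what was meant, but the operative sentence names stopping vaccine as a trigger in its own right, so the correct reading depends on inference.

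The defence also limits the consequences, and these limits stand:

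- The original event is not abandoned. SAEs, AESIs and events that led to withdrawal are followed after discharge (Sections 9.1 and 12.5.11.1.2), pregnancies are followed to outcome (12.5.11.2), and related SAEs that come to light later are reported (8.4.4). What is lost is active ascertainment of new events.
- Safety is descriptive, with no between-group tests.
- Section 8.6.1 asks for its procedures when possible and sets no day for the blood draw, so an immediate draw is not prescribed. Many stops would be established at Visit 3 or Visit 4, when eligibility is rechecked.
- Keeping a subject does not guarantee per-protocol value: SAP code 2170 removes pregnancies found at Visit 1 or Visit 3, and code 2050 may remove others.

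A reader might go further and infer that co-primary samples are generally lost. Step 3 of the working shows that they are not. A reader might also infer that the co-administration arm loses more follow-up because only it receives two active vaccines at Visit 1. That would require an excess of stopping in that arm, and nothing in the documents shows one.

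**Conclusion.** The contradiction is real and should be corrected. Its main effect is on safety: a subject closed under 8.6.1 at Day 10, 61 or 91 loses 97%, 78% or 67% of the Day 1 to Month 9 period for detecting new SAEs, AESIs and medically attended AEs, and such subjects may have been selected by a safety event. This rests on the site applying 8.6.1 as written instead of 7.7, 9.1 or 9.2. The immunogenicity effect is confined to stops and draws within about 23 days of dose 1 or of the Visit 3 dose, and the effect on power is negligible.

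No total can be given. It is tempting to apply a stopping rate such as 1–3% to 945 subjects and report 9 to 28 affected. That rate is not in the documents, and the count would also assume that every subject who stops vaccination is closed, against the other sections.

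**What to change.** Limit Section 8.6.1 to subjects whose study participation ends, by striking the treatment-withdrawal trigger from its opening sentence. Subjects who only stop vaccination and agree to continue then keep the contacts already scheduled for them: any Visit 2 or Visit 4 sample still due, Visit 5, and the safety calls to Day 271 or Day 451 as applicable. The termination page is completed only at their last contact.

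Reconcile 8.6.1 with Sections 7.7, 9.1, 9.2 and 12.5.7.1 so that all five describe the same status. Check SAP code 2050 in the same pass: it excludes from the per-protocol sets subjects who met withdrawal criteria but were not withdrawn, and it should not conflict with protocol text that encourages subjects to stay.

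Leave unchanged the rules on who stops vaccination and the investigator's discretion over individual procedures. The cost is a wording change and a memo to sites, plus a few more calls and samples that the schedule already contains.

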8.7. Study procedures during special circumstances

During special circumstances (e.g., COVID-19 pandemic), the specific guidance from local public health and other competent authorities regarding the protection of individuals' welfare must be applied. For the duration of such special circumstances, the following measures may be implemented for enrolled subjects:

- If the eDiary device was provided to the subject, it may be returned to the site by conventional mail after the end of the relevant data collection period (Visit 5).
- Biological samples may be collected at a different location* other than the study site or at subject's home. Biological samples should not be collected if they cannot be processed in a timely manner or appropriately stored until the intended use.

*It is the investigator's responsibility to identify an alternate location. The investigator should ensure that this alternate location meets ICH GCP requirements, such as adequate facilities to perform study procedures, appropriate training of the staff and documented delegation of responsibilities in this location. This alternate location should be covered by proper insurance for the conduct of study on subjects by investigator and staff at a site other than the designated study site. Refer to local regulatory guidance on conduct of clinical trials during COVID-19.

Impact on the Per Protocol Set (PPS) for immunogenicity will be determined on a case by case basis.

9. DISCONTINUATION CRITERIA

9.1. Discontinuation from the study

From an analysis perspective, a 'withdrawal' from the study refers to any subject who was not available for the concluding contact foreseen in the protocol.

All data and samples collected until the date of withdrawal/last contact of the subject will be used for the analysis.

A subject is considered a 'withdrawal' from the study when no study procedure has occurred, no follow-up has been performed and no further information has been collected for this subject from the date of withdrawal/last contact.

Investigators will make an attempt to contact those subjects who do not return for scheduled visits or follow-up.

Primary reason for study withdrawal will be documented in the eCRF. The investigator will document whether the decision to withdraw a subject from the study was made by

the subject himself/herself, by the subject's parent(s)/LAR(s), or by the investigator, as well as which of the following possible reasons was responsible for withdrawal:

- SAEs requiring expedited reporting (please refer to section [12.5.9.2](#) for the details)
- Unsolicited non-serious AE
- Solicited adverse event
- Protocol deviation
- Withdrawal by subject, not due to an adverse event*
- Migrated/Moved from the study area
- Lost to follow-up
- Sponsor study termination
- Other (specify)

*In case a subject is withdrawn from the study because he/she/the subject's parent(s)/LAR(s) has withdrawn consent, the investigator will document the reason for withdrawal of consent, if specified by the subject/subject's parent(s)/LAR(s), in the eCRF.

Subjects who are withdrawn from the study because of SAEs/AEs must be clearly distinguished from subjects who are withdrawn for other reasons. Investigators will follow subjects who are withdrawn from the study as result of a SAE/AE until resolution of the event (see Section [12.5.11](#)).

The reasons for premature withdrawal from the study include adverse event, death, withdrawal of consent, lost to follow-up, administrative reason, and protocol deviation. These reasons are described in greater detail below.

Adverse Event:

For any subject withdrawn from study participation prior to the planned Study Termination Call, it is important to determine if an AE was associated with the reason for discontinuing the study. This AE must be identified on the AE eCRF page by indicating "Withdrawn from study due to AE". Any ongoing AEs at the time of study withdrawal must be followed until resolution or stabilization.

Subjects who develop a SAE judged to be possibly related to the study vaccine, including hypersensitivity reactions, should not receive subsequent vaccination.

Death:

For any subject withdrawn from study participation due to death, this should be noted on the Study Termination eCRF page and the associated SAE that led to the death must be reported.

Withdrawal of consent:

The subject and/or parent(s)/LAR(s) can withdraw consent for participation in the study at any time without penalty or loss of benefit to which the subject is otherwise entitled. Reason for early termination should be deemed as “withdrawal of consent” if the subject withdraws from participation due to a non-medical reason (i.e., reason other than AE). If the subject and/or parent(s)/LAR(s) intend(s) to withdraw consent from the study, the investigator should clarify if the subject will withdraw completely from the study or if the subject will continue study participation for safety, or a subset of other study procedures. If the subject requests complete withdrawal from the study, no further study interventions will be performed with the subject.

If a subject and/or parent(s)/LAR(s) withdraw(s) consent but does not revoke the HIPAA (The Health Insurance Portability and Accountability Act) authorization, the Sponsor will have full access to the subject’s medical records, including termination visit information. If a subject and/or parent(s)/LAR(s) revokes only the HIPAA authorization, the Sponsor will have full access to all of the subject’s medical records prior to the date and time of written revocation.

Lost to Follow-Up:

For subjects who are not accessible through call for final visit (study Day 451), or for 2 consecutive visits, study staff are encouraged to make at least 3 documented attempts to contact the subject by telephone and at least one documented written attempt to contact the subject and/or parent(s)/LAR(s) to encourage the completion of study termination procedures. These efforts to contact the subject should be recorded in the source document. The termination date for the subject to be captured on the Study Termination eCRF page is the date of the last successful contact (clinic visit or telephone) with the subject. Please refer to Section [9.3](#) for further details.

Administrative Reason:

Examples for subjects withdrawn from the study due to administrative reason can include: Sponsor decision to terminate the study, subject meeting a pre-specified withdrawal criterion, subject discontinuation for insurance issues, moving, no time, etc. This reason should be noted in the Study Termination eCRF page and any ongoing AEs at the time of study withdrawal must be followed until resolution/stabilization.

If the clinical study is prematurely terminated by the Sponsor, the investigator is to promptly inform the study subjects and local EC/IRB and should assure appropriate therapy and follow up for the subjects. All procedures and requirements pertaining to the archiving of study documents should be followed. All other study materials (study medication/vaccines, etc.) must be returned to the Sponsor.

For subjects who are withdrawn from the study due to receipt of an excluded medication/vaccination or due to significant protocol non-compliance, this reason should be noted in the Study Termination eCRF page.

Protocol Deviation:

A protocol deviation is any change, divergence, or departure from the study design or procedures of a study protocol. In general, subjects associated with protocol deviations may remain in the study unless continuation in the study jeopardizes the subject's health, safety, or rights.

Investigators will apply due diligence to avoid protocol deviations. Under no circumstances should the investigator contact GSK or its agents, if any, monitoring the study to request approval of a protocol deviation, as no authorized deviations are permitted. If the investigator feels a change to the protocol would improve the conduct of the study this must be considered a protocol amendment, and unless such an amendment is agreed upon by GSK and approved by the IRB/EC and health authorities it cannot be implemented.

Any subject who becomes pregnant during the study, despite the protocol requirement for highly effective method of contraception, will not receive further vaccinations but should be encouraged to continue participating in the study for safety follow-up. The site must complete a Pregnancy Report eCRF (initial report) as soon as possible after learning of pregnancy occurrence (see Section 12.5.8 for further details). If the subject withdraws from the study for any of the above categories except death, the site will obtain permission from the subject to continue to remain in contact with her until the outcome of the pregnancy is known, even if the outcome is not known until after the subject reaches the end of follow-up period.

